Description of Problem to be Solved: Severe obesity, defined as having a body mass index (BMI) \geq 120% of the 95th percentile, continues to rise among children and adolescents, with one-third of obese children currently being classified as severely obese.1 Racial disparities in severe obesity exist: African American children have a 2 to 3 times higher prevalence of severe obesity than White children.7 Though the role of physical inactivity as a contributor to the development of obesity is well established, we know far less about how obesity alters physical activity levels. Considering 17% of children are obese, we urgently need to identify the impact of obesity on children's physical activity so that we can intervene early in the disease. The Scientific Report of the 2015 Dietary Guidelines Advisory Committee4 recommends increasing physical activity and reducing sedentary behavior as a way to manage weight. Further, physical activity is recommended as first-line obesity treatment for children.8 Yet only 8% of 12-15 year-olds meet national physical activity guidelines of 60 minutes of daily moderate-to-vigorous physical activity (MVPA).9 Our research team has demonstrated that adolescents instead spend 7.5 hours per day sitting, with sitting more common among obese youth.10 Physical activity programs are often hindered by high attrition (27% to 73% in a recent review11), due to inconvenience, transportation barriers, and scheduling conflicts.12,13 Our project examines the influence of body fat and fat accumulation on the presence, proximity, location, and timing of physical activity and sedentary behavior in a child's day and whether these patterns vary by race. By examining facilitators to and barriers of physical activity, our project will inform new strategies about how to target children to increase physical activity and reduce sedentary behavior, particularly those children who rapidly accumulate body fat.

Background

Research Gaps

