The hypotheses will be tested using a series of generalized linear models with severe obesity as the independent variable. First, linear mixed effect models will be used to test for effects between BMIz and each dependent continuous variable (change in: min/day sedentary behavior, min/day MVPA, and each cardiometabolic risk factor). Next, logistic regression models will be used to determine the association between BMIz with the likelihood of not meeting recommended behaviors (i.e. top quartile of min/day of sedentary behavior; MVPA < 60 min/day) or being at elevated cardiometabolic risk. Finally, the cohort will be stratified into two groups based on obesity at Year 0: severely obese (SO) and not severely obese (NSO). Logistic regression models will be used to determine associations between SO (vs. NSO) and each dependent variable (i.e. change in: minutes/day sedentary time, minutes/day MVPA, and each continuous cardiometabolic risk factor). Covariates will include age, sex, dietary intake, and race. School

term vs. school holiday will be considered as an additional covariate if time of year is significantly associated with the independent and dependent variables.

Secondary analysis will use MRI and DXA as covariates in the model (namely the visceral, trunk, and total body fat). These measurements, along with BMIz, may be highly correlated. Various variable select criteria (including LASSO and support vector machine) will be used to determine which combination of these variables best explains the variance in the data. The full model will enable the comparison of imaging-based body composition measures vs. BMIz alone and their associations with physical activity, sedentary behavior, and cardiometabolic risk factors in children.

As exploratory analyses, dietary intake will be tested as a potential mediator to explain significant associations between the predictor variable (BMIz) on outcomes (physical activity, sedentary behavior, and cardiometabolic risk factors). Series of sequential models will be used to test each pathway using a path analysis model based on the Baron and Kenny causal steps for mediation.73,74

Objective 2:

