The primary outcome for the first objective is change in minutes of sedentary behavior between Year 0 and Year 2 (i.e. Year 2 values minus Year 0 values). Baseline estimates for the two groups were calculated using the WAIST cohort data (from the 2010-11 assessment). Based on data from Berkey et al.,75 the SO group is assumed to increase their sedentary time by 30 minutes/day at year 2, while smaller increases in sedentary time is expected for the NSO group (**Table 5**). A minimum of 334 participants is needed to ensure a well-powered study with significance level of $\alpha = 0.05$, 80% power to detect a 24 minute difference change in sedentary behavior between the two groups, and allowing for a dropout rate of 25%. Therefore, our sample size of up to 345 participants will be sufficient.

Change in minutes/day of sedentary time for NSO group	Change in minutes/day of sedentary time for SO group	Difference in change between groups	Standard deviation of change between groups	Minimum sample size	Total sample size (allows for 25% dropout)
2.4	30.0	27.6	69.6	202	253
3.6	30.0	26.4	69.6	222	278
4.8	30.0	25.2	69.6	242	303
6.0	30.0	24.0	69.6	266	334

Table 5. Difference in changes in sedentary time based on severe obesity status. *Note.* NSO is the group classified as not severely obese; SO is the group classified as severely obese.

Note. NSO is the group classified as not severely obese; SO is the group classified as severely obese.

Secondary analyses will include change in daily MVPA minutes between years and change in days/week of physical activity (\geq 60 minutes MVPA/day) between years. Power analysis was conducted on these outcomes, using the WAIST cohort and data from Nigg et al.,76 and our sample size will have power of 93.8% and 90.4% to detect a significant difference in change in daily MVPA minutes and change in days/week of physical activity, respectively.

Contingencies

Based on national reference data, it is possible that very few or no severely obese children meet the healthy behavior or cardiometabolic health criteria (e.g. no severely obese child attains ≥ 60 minutes of MVPA/day; no severely obese child has a waist circumference < 90th percentile). If this is the case, the dichotomous dependent variable will be adjusted to be quartiles, so that the analyses is interpreted as the likelihood of a severely obese child being in the top (healthiest) quartile of the health behavior or cardiometabolic health criteria for the overall cohort.

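### The sparse-data contingency replaces the guideline outcomes of Objective 1 with a cohort quartile on an unnumbered count in the severely obese group, and keeps no guideline result

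*Combined protocol and SAP*

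**What the plan says.** Statistical Analysis, Objective 1, plans logistic models relating BMIz to "the likelihood of not meeting recommended behaviors (i.e. top quartile of min/day of sedentary behavior; MVPA < 60 min/day") or to elevated cardiometabolic risk. A further set compares severely obese (SO) with not severely obese (NSO) children: "Logistic regression models will be used to determine associations between SO (vs. NSO) and each dependent variable". The dependent variables listed there are continuous changes, not the guideline categories.

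The Contingencies paragraph under Power analysis, Objective 1, anticipates, citing national reference data, that "it is possible that very few or no severely obese children meet the healthy behavior or cardiometabolic health criteria". One of its two examples is that "no severely obese child has a waist circumference < 90th percentile"; the other is that no severely obese child reaches 60 minutes of MVPA a day. In that event "the dichotomous dependent variable will be adjusted to be quartiles, so that the analyses is interpreted as the likelihood of a severely obese child". The outcome whose likelihood is then modelled is "being in the top (healthiest) quartile of the health behavior or cardiometabolic health criteria for the overall cohort".

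No count or percentage defines very few and no visit is named. Nothing says that the guideline result would still be reported, or that a sparse-data method would be tried first.

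The primary outcome lies outside this rule: "The primary outcome for the first objective is change in minutes of sedentary behavior between Year 0 and Year 2".

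**The concern.** The dependent variable would be settled after looking at how many exposed children have the outcome. Because very few is undefined, the analyst makes that call with the count in view. It would be made criterion by criterion, so one report could mix guideline and quartile odds ratios.

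The replacement also answers a different question. Sixty minutes a day and the cardiometabolic cut-offs are external standards. The healthiest quartile is defined within a sample deliberately recruited at about 50% severe obesity (Number of Participants), so its cut-off has no meaning outside this cohort and does not bear on the recommendation that motivates the study. At stake are the meaning and size of a reported secondary odds ratio, and whether the guideline answer appears at all.

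**Working it through.** **1. Group size.** The contingency states no figure, so Table 5 is used to anchor n. For a 24 min/day difference, SD 69.6, two-sided alpha 0.05 (sidedness assumed) and 80% power, n per group = 2 × (1.960 + 0.842)² × (69.6/24)² = 2 × 7.849 × 8.41 = 132.02. This rounds up to 133, or 266 in total, which reproduces the table. With 345 enrolled and 25% dropout, 345 × 0.75 ≈ 258 remain, about 129 per group at a 1:1 split.

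**2. How often the trigger is met.** The SO count is Binomial(129, p), so P(0) = (1 − p)^129. The rates p are assumptions; the plan gives none for severely obese children.

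| True SO rate | P(0) | P(≤2) | P(≤3) |
|---|---|---|---|
| 1% | 27% | 86% | 96% |
| 2% | 7% | 52% | 74% |
| 3% | 2% | 25% | 46% |
| 5% | 0.1% | 4% | 11% |

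At 1% to 3%, whether the switch happens depends mainly on whether very few means none, two or three.

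**3. Does the trigger track the association?** Description of Problem to be Solved says that "only 8% of 12-15 year-olds meet national physical activity guidelines". Take 8% as the assumed NSO rate, with normal MVPA and the SO mean shifted down by d SD. The SO rate is then 1 − Φ(1.405 + d):
- d = 0.3: 4.4%, P(0) = 0.3%
- d = 0.6: 2.2%, P(0) = 5%
- d = 1.0: 0.8%, P(0) = 35%
- d = 1.3: 0.3%, P(0) = 64%

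The trigger becomes much more likely as the association grows. It does not look at the NSO group, however. With the same 2% in both groups, P(≤3) is still 74%.

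**4. What the switch does to the estimate.** Odds ratios here are for meeting the criterion, NSO relative to SO, with equal groups and normal MVPA of equal variance.
- 1% v 8%: guideline OR = (0.08 × 0.99)/(0.01 × 0.92) = 8.6. The implied shift is 2.326 − 1.405 = 0.921 SD. The pooled upper-quartile cut-off then leaves 11.3% of SO and 38.7% of NSO children above it, so the quartile OR = (0.387 × 0.887)/(0.113 × 0.613) ≈ 4.9.
- 1% v 15%: guideline OR = (0.15 × 0.99)/(0.01 × 0.85) = 17.5. The shift is 1.290 SD and the upper-quartile shares are 7.1% and 42.9%, giving a quartile OR of 9.8.

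**5. Is the guideline outcome still analysable?** For an SO v NSO table with an empty cell, take 0/129 v 10/129 (10/129 is about 8%). Fisher's exact p = 0.0016. Adding one half to each cell, OR (SO relative to NSO) = (0.5 × 119.5)/(129.5 × 10.5) = 0.044. The standard error of its log is √(1/0.5 + 1/10.5 + 1/129.5 + 1/119.5) = 1.453, giving a 95% interval of 0.003 to 0.76. This is a Wald approximation; a penalised profile-likelihood interval would differ. With no SO events, 6/129 in NSO gives p = 0.029, 5/129 gives p = 0.060 and 2/129 gives p = 0.50.

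For the BMIz model that the plan actually specifies, an empty SO group need not cause separation, because NSO children who do and do not meet the criterion overlap in BMIz. In 500 simulated cohorts (SO: BMIz mean 2.5, SD 0.25, no events; NSO: mean 0.8, SD 0.9, 8% events; all assumed), ordinary logistic regression converged every time.

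**The case against.** The contingency is written in advance and gives a reason. A fallback for an empty cell is sensible in principle, since ordinary maximum likelihood gives no finite odds ratio for an SO v NSO table with a zero cell. Its reach is limited: the primary outcome, change in MVPA and the continuous risk factors are untouched, and the sedentary-time category is already a quartile with no external standard to lose. All of this stands, and it keeps the point to secondary analyses.

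A reader might infer that the plan discards its answer exactly when the association is strongest. The documents do not support that. The rule counts only severely obese children, so it can also fire when the behaviour is rare in everyone; 0 v 2 of 129 is no evidence of association.

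A reader might also infer a post hoc swap that inflates type I error. The fallback is prespecified, though incompletely. When the rule was simulated with no association (common rates from 2% to 25%; switch at 0, 3 or 6 or fewer SO events; Fisher tests), overall rejection stayed below 5% in every scenario. Nor does the switch cost power: in simulations with NSO at 8% and a 1 SD shift, power was 78% for the guideline outcome and about 100% for the quartile.

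Finally, top means most sedentary in the analysis section and healthiest in the contingency. Each use is clear in its place, so this is not a contradiction.

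What the objection does not answer is that the trigger has no number, depends on the exposed group's outcome, and leaves no guideline result.

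**Conclusion.** The point holds for the secondary dichotomous outcomes of Objective 1 that rest on an external criterion: MVPA below 60 min/day and the cardiometabolic criteria. Followed as written, the plan can replace a guideline odds ratio with one roughly 40% smaller (8.6 to 4.9, or 17.5 to 9.8) and different in meaning, on a difference of one to three children and an unstated reading of very few. The harm is to the estimand and to completeness of reporting, not to error control. The odds ratios rest on normal MVPA with equal variances and equal groups, and the trigger probabilities on 129 severely obese children and assumed rates of 1% to 5%. The absence of a threshold and of a retained guideline result depends on none of these. It is an inexpensive improvement to the plan and does not threaten the main result.

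**What to change.** Remove the substitution from the Contingencies paragraph and state instead:
- Guideline counts and percentages are reported for SO and NSO children at each visit, whatever they are.
- The guideline models in Statistical Analysis, Objective 1, are always fitted and reported. Where cells are sparse, Firth-penalised logistic regression with profile-likelihood intervals, or exact logistic regression, is used.
- The healthiest-quartile analysis is reported in all cases as a prespecified supplement, labelled as relative to this cohort.

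The same edit should say whether the guideline categories are modelled on BMIz, on SO v NSO, or both, since the analysis section and the contingency differ on this.

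The cost is a few sentences and slightly more analysis in the SAS software already named. The downside is wide intervals when events are few, which is an honest reflection of the data.

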We will include adolescents aged 10 to 16 years. We selected this age range because adolescence is a developmental period of rapid fat gain and changes in activity patterns. By choosing the maximum age as 16 years at baseline, the children are likely to still live in Baton Rouge and attend high school at the second clinic visit (age 18 years), facilitating follow-up.

Inclusion Criteria:

- Age 10-16 years
- Body weight < 500 lbs.
- Ability to understand instructions and complete all study procedures

Exclusion Criteria:

- Pregnant
- On a restrictive diet due to illness
- Significant physical or mental disabilities that impede walking, wearing accelerometer or GPS, or responding to EMA.

In addition to the exclusion criteria listed above, participants who refuse to provide written assent, or whose parents or legally authorized representative refuse to sign an informed consent document, will be excluded from the study. Consent/assent will be obtained upon each participant's arrival at the PBRC Pediatric Research Clinic before participating in any study procedures. To further safeguard participant safety and internal validity of the study, inclusion and exclusion criteria will be reassessed by PBRC clinic staff following the completion of required assent/consent forms. The principal investigator and medical investigator have the right to withdraw a participant from the study at any point for any reason.

Number of Participants

We will identify and recruit up to 345 boys and girls aged 10 to 16 years. The sample will be screened on the telephone in attempt to achieve a comparable sex and race distribution. We will oversample for severely obese youth so they comprise approximately 50% of the sample (with the other 50% being distributed among normal weight, overweight, and obese status).

Recruitment Methods

Recruiting children for clinical studies is challenging, particularly those from high risk populations such as with severe obesity and from ethnic minority groups. However, we are confident we can recruit up to 345 children within 2 years. A key recruitment strategy will be to enroll participants who completed the WAIST Study.¹⁶ Of 423 initial participants who were assessed for the WAIST Study in 2010-11, 386 (91.3%) agreed to be re-contacted. Of these, 193 participants will meet the age criteria for the follow-up

Page 7 of 35

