Objective 2:

The primary outcome for the second objective is the relationship between total fat accumulation and change in sedentary behavior. Based on data from Berkey et al.,75 we estimate an overall change in sedentary behavior of 12 minutes/day increase in the HFG and 3.6 minutes/day increase in the LFG over a two-year period. **Table 6** shows sample sizes required to detect various differences for the change between groups. With a sample size of up to 345, this will provide at least 80% power for detecting a difference in the change between groups of 8.4 minutes/day, allowing for the anticipated 25% dropout. Therefore, with our sample size of up to 345 participants, we will have sufficient power to detect a difference between the HFG and LFG groups.

Change in minutes	Change in minutes	Change between	Standard deviation	Minimum sample	Total sample size
of sedentary time	of sedentary time	groups	of change between	size	(allows for 25%
for HFG	for LFG		groups		dropout)
12	2.4	9.6	24	194	259
12	3	9.0	24	220	293
12	3.6	8.4	24	255	Up to 345
12	4.2	7.8	24	292	389

Table 6. Difference in changes in sedentary time between the high fat vs. low fat gainer group. *Note.* HFG is the group classified as high fat gainers; LFG is the group classified as low fat gainers.

Secondary analyses based on the second objective will include modeling the relationship between fat mass accumulation and change in physical activity. Using data from Berkey et al.,75 we estimate an overall decrease of 19.2 minutes/day of MVPA in the HFG and a decrease of 4.8 minutes/day of MVPA in the LFG over a two-year period. With a sample size of up to 345 (including anticipated dropout), this will provide 93.4% power for detecting a difference in the change between groups of 14.4 minutes/day.

Contingencies

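### Tables 5 and 6 assume group mean changes in sedentary time that cannot all hold in one cohort with about 50% severe obesity

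*Combined protocol and SAP*

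**What the plan says.** Under Power analysis, Objective 1: "The primary outcome for the first objective is change in minutes of sedentary behavior between Year 0 and Year 2". For the planning values, "the SO group is assumed to increase their sedentary time by 30 minutes/day at year 2", and the NSO group is expected to rise too, by less: 2.4, 3.6, 4.8 or 6.0 min/day across the four rows of Table 5. The row that sets the minimum enrolment of 334 reads "6.0 30.0 24.0 69.6 266 334" (NSO change, SO change, difference, SD, minimum N, N with dropout).

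Under Power analysis, Objective 2: "The primary outcome for the second objective is the relationship between total fat accumulation and change in sedentary behavior". There, "we estimate an overall change in sedentary behavior of 12 minutes/day increase in the HFG and 3.6 minutes/day increase in the LFG", over two years. Table 6 fixes the high fat gainers (HFG) at 12 and varies the low fat gainers (LFG) from 2.4 to 4.2, with an SD of 24.

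The Objective 2 analysis forms HFG and LFG by a percentile division of the group on change in total body fat, with no cut point given. Number of Participants fixes the other division: "We will oversample for severely obese youth so they comprise approximately 50% of the sample". Both power sections cite reference 75 for the changes, allow 25% dropout and are judged against enrolment of up to 345.

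**The concern.** A cohort has one mean change however it is divided. SO/NSO and HFG/LFG are two divisions of the same children on the same outcome, so the weighted average of the two group means must agree between the tables. It does not.

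This matters because these means are the plan's stated reason for calling 345 sufficient for both primary outcomes. A reader cannot tell which expected change the study was designed around, or how one cited source gave two sets of values that do not fit together. If the lower set is nearer the truth, the 24-minute difference behind the 334 is hard to reach.

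**Working it through.** **Inputs.** Table 5: SO 30; NSO 2.4 to 6.0; SD 69.6; N 266 in the row that sets 334. Table 6: HFG 12; LFG 2.4 to 4.2 (3.6 in the planned row); SD 24; N 255. SO share about 50% (Number of Participants). Alpha 0.05 and 80% power are stated for Objective 1. A two-sided test, and the same alpha for Objective 2, are assumptions.

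**1. Reproduce the plan's sample sizes.** n per group = 2 × (SD × 2.802 / difference)².
- Table 5: 2 × (69.6 × 2.802 / 24)² = 132.0, rounded up to 133, so 266 in total. Stated: 266.
- Table 6: 2 × (24 × 2.802 / 8.4)² = 128.1, rounded up to 129, so 258 in total. Stated: 255, close enough.

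Each N follows from its own difference and SD. The conflict lies in the means behind them.

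**2. Cohort mean under Table 5.** Mean = p × SO + (1 − p) × NSO, with p = 0.5.
- NSO 2.4: (30 + 2.4)/2 = 16.2
- NSO 3.6: 16.8
- NSO 4.8: 17.4
- NSO 6.0: 18.0 (the row that sets 334)

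**3. Cohort mean under Table 6.** At a median split: (12 + 2.4)/2 = 7.2 up to (12 + 4.2)/2 = 8.1, and 7.8 in the planned row. At any other split the mean lies between the two group means, so it cannot exceed 12. The missing cut point does not matter.

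**4. Sensitivity to the SO share (NSO 6.0).**
- 40% SO: 0.4 × 30 + 0.6 × 6 = 15.6.
- All 25% dropout from the SO group: share (0.50 − 0.25)/0.75 = 33%, mean 14.0.
- To reach 12, the share must fall to (12 − 6)/(30 − 6) = 25%, half the target.
- In the 33% case the NSO 2.4 row does fall below 12, to 11.6, but nearly every child would then have to be HFG.

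**5. Children excluded from scans.** Suppose 12% of those analysed in Table 5 fall outside Table 6, and the rest are at Table 6's ceiling of 12. Their mean rise would have to be (18.0 − 0.88 × 12)/0.12 = 62 min/day, or (16.2 − 0.88 × 12)/0.12 = 47 for the lowest row. Neither is plausible beside an assumed SO rise of 30.

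**6. If Table 6 holds.** At 50% SO and cohort mean m, SO = 2m − NSO, so the difference is 2m − 2 × NSO. If NSO does not fall (NSO ≥ 0), the difference is at most 2m.
- m = 7.8: at most 15.6. Two-sample t-test power at n = 266, SD 69.6: 44%.
- Any split: m is below 12 as long as there are any low gainers, so the difference is below 24.

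Conditional on one of Table 5's own NSO values:

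| NSO held at | Cohort mean | SO-NSO difference | Power (n=266, SD 69.6) |
|---|---|---|---|
| 6.0 | 12 (ceiling) | 12 | 29% |
| 2.4 | 7.8 | 10.8 | 24% |
| 6.0 | 7.8 | 3.6 | 7% |

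**7. If Table 5 holds.** With a cohort mean of 18.0 and equal groups, HFG 22.2 and LFG 13.8 average to 18.0 and still differ by 8.4. Both means change; the difference need not.

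**8. The SDs.** The two tables also use 69.6 and 24 for the SD of the same outcome. With SD 69.6, a difference of 8.4 needs 2 × 1,078 = 2,156 children, and about 255 give 16% power. With SD 24, a difference of 24 needs only 32.

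**The case against.** The strongest reply is that sample size depends on the difference and the SD, not on the cohort mean. Differences of 24 and 8.4 can both occur around one mean: at 7.8, SO 19.8 and NSO −4.2 differ by 24. Holding SO at 30 with a cohort mean of 12 gives NSO −6, a difference of 36 and about 99% power. So the low powers in the table above depend on which mean is held fixed.

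Much of this stands. A reader might infer that one table's effect size is impossible under the other; the documents do not support that for the 8.4-minute difference, which survives if both fat-gain means move. The 29%, 24% and 7% powers hold only at the stated NSO values. For the 24-minute difference, however, each escape needs NSO sedentary time to fall, while the plan expects it to rise. Some of the plan's written assumptions must go either way.

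Two further inferences fail. One might hold HFG at 12 under Table 5's mean, find LFG at 20.4 to 24.0, and say that Hypothesis 2 is reversed. Hypothesis 2 states an association without a direction, and holding LFG at 3.6 instead gives HFG 28.8 to 32.4. One might also treat 62 min/day as the least that excluded children would need; it is 47 in the lowest row.

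It is also fair to say that both tables are multi-row scenarios, that baseline estimates came from the WAIST cohort, and that the derivation from reference 75 cannot be seen. No row of either table removes the conflict at 50% SO.

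**Conclusion.** The conflict is real. At about 50% SO, the assumed means imply a cohort rise of 16.2 to 18.0 min/day in Table 5 and at most 12 in Table 6 (7.2 to 8.1 at a median split), so they cannot all be right. If Table 6 is right and NSO sedentary time does not fall, Objective 1's difference is at most 15.6 at the planned mean of 7.8, with about 44% power rather than 80%, and is below 24 at any split. If Table 5 is right, both Table 6 means are wrong, but its 8.4-minute difference may stand.

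This rests on an SO share near 50% among those analysed, unadjusted group means, and a two-sided 5% test. The conflict in means does not by itself show that either sample size is wrong. The documents do not show which table is nearer the truth. The plan should be corrected on this point, but the study design is not in question.

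**What to change.** Derive both tables from one stated set of inputs:
- the expected cohort mean change;
- the SO share and the HFG share, with the fat-gain cut point;
- one SD of two-year change in sedentary minutes, in place of 69.6 and 24;
- the figure taken from reference 75, with the time span it covers and how it was scaled to two years.

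Show that both divisions average to the same cohort mean. Then restate the planned difference and the power for each objective at 345 enrolled with 25% dropout. The SD must be included: moving the means while keeping differences of 24 and 8.4 would leave both sample sizes as they are and the SD conflict unresolved.

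The cost is rework of two planning tables and the text around them. Enrolment and procedures do not change. The stated power for an objective may fall and should then be reported as it is.

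### Tables 5 and 6 plan the same outcome in the same cohort with SDs of 69.6 and 24 min/day, so at least one primary power statement is wrong

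*Combined protocol and SAP*

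**What the plan says.** The Power analysis section treats change in sedentary time as the primary outcome twice.

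- **Objective 1 (Table 5).** "The primary outcome for the first objective is change in minutes of sedentary behavior between Year 0 and Year 2". Severely obese (SO) participants are compared with the rest (NSO). Every row uses an SD of 69.6 min/day, under the heading "Standard deviation of change between groups". The planning row has a difference of 24.0, 266 analysed and 334 in total. The text says "A minimum of 334 participants is needed to ensure a well-powered study", "allowing for a dropout rate of 25" per cent, and concludes: "Therefore, our sample size of up to 345 participants will be sufficient".
- **Objective 2 (Table 6).** "The primary outcome for the second objective is the relationship between total fat accumulation and change in sedentary behavior". High fat gainers (HFG) are compared with low fat gainers (LFG). Every row uses an SD of 24 min/day, under the same column heading. The planning row has a difference of 8.4, 255 analysed and up to 345 in total. The text claims "at least 80% power for detecting a difference in the change between groups of 8.4 minutes/day, allowing for the anticipated 25% dropout" and concludes that "we will have sufficient power to detect a difference between the HFG and LFG groups".

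The section names the earlier WAIST cohort as the source of Objective 1's baseline estimates, and a cited study of one-year changes as the source of the mean changes in both objectives. It attributes neither SD to a source.

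**The concern.** Both tables describe the spread of one variable in one set of children, and the SDs differ by a factor of 2.9. Required sample size scales with variance, so the implied sample sizes differ by a factor of about 8.4. At least one of the two power statements for a primary outcome must therefore be wrong.

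The main stake is how Objective 2 is read. If the SD is near 69.6, a null comparison of high and low fat gainers says very little, yet the plan calls the power sufficient. If the SD is near 24, Objective 2 stands but Objective 1's stated minimum is greatly overstated. As written, a reader cannot tell which applies.

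**Working it through.** **Inputs.** Differences, SDs and Ns are from Tables 5 and 6. Alpha of 0.05 and 80% power are stated for Objective 1. The 25% dropout is from Anticipated Dropout. The roughly 1:1 SO/NSO split is from Number of Participants. Assumed: a two-sided test throughout, and alpha 0.05 with a 1:1 split for Objective 2, where the plan says only that percentiles will be used. Analysed N: 345 × 0.75 = 258.75, so 258.

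**Step 1. Reproduce the plan's Ns.** Method: two-sample t-test, two-sided 0.05, 80% power, equal groups. The normal approximation is total N ≈ 4(1.96 + 0.84)² × (SD/difference)².

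| Table | SD | Recomputed N | Stated N |
|---|---|---|---|
| 5 | 69.6 | 202, 222, 242, 266 | 202, 222, 242, 266 |
| 6 | 24 | 200, 226, 260, 300 | 194, 220, 255, 292 |

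Table 5 is exact. Table 6 agrees within about 3%; its stated Ns give 79.0% to 79.5% power by this method. Each table therefore follows from its own SD, and the conflict lies in the SDs.

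**Step 2. Can both SDs be true?**
- *Different grouping.* Table 5 implies a total SD of √(69.6² + 12²) = 70.6, where 12 is half the 24-minute gap. Splitting the same children into two equal groups 8.4 apart leaves a within-group SD of √(70.63² − 4.2²) = 70.5, not 24.
- *Covariates.* Adjustment would have to remove 1 − 24²/70.50² = 88% of the variance. The Statistical Analysis section lists the same covariates (age, sex, dietary intake, race) for both objectives.
- *Different analysed sets.* Suppose Objective 1 keeps 300 (345 × 0.87) and Objective 2 keeps 258 of them. If the 258 had SD 24, the other 42 would need √((300 × 70.63² − 258 × 24²)/42) ≈ 179 min/day. This assumes equal means and is illustrative.

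**Step 3. Objective 2 power for 8.4 min/day, 258 analysed.**

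| SD | 24 | 30 | 40 | 50 | 60 | 69.6 |
|---|---|---|---|---|---|---|
| Power | 80% | 61% | 39% | 27% | 20% | 16% |

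At SD 69.6 the difference detectable with 80% power is about 24.4 min/day, and 80% power for 8.4 would need about 2,156 analysed. Changing the assumptions does not rescue it: power is 15% at a 1:2 split, 13% at 1:3, and 25% for a one-sided test at 1:1 with 255 analysed. The expected 95% CI half-width, t × SD × √(2/129), is 5.9 min/day at SD 24 and 17.1 at 69.6.

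**Step 4. Objective 1 for 24 min/day.**
- At SD 24: 34 analysed, and 34/0.75 = 45.3, so 46 enrolled, against the stated 266 and 334.
- At SD 69.6, the dropout allowance is wrong. Table 5's totals (253, 278, 303, 334) are close to N × 1.25 (252.5, 277.5, 302.5, 332.5). Allowing for 25% loss requires N/0.75: 270, 296, 323, 355. Table 6 does divide: 194/0.75 = 258.7, 220/0.75 = 293.3 and 292/0.75 = 389.3, printed as 259, 293 and 389.
- The stated 334 covers a loss of only 1 − 266/334 = 20.4%. With 25% loss, 334 leaves 250 (77.5% power) and 345 leaves 258 (78.8%).

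**The case against.** The strongest reply concerns weight. On the plan's own timetable recruitment was to end in spring 2018, and this version is dated March 2021. The correction changes no data, model or enrolment, and a null result can be read from its confidence interval whatever Table 6 says. The harm is also one-sided: if 24 is right, Objective 2's claim stands and 345 is more than enough for Objective 1. This limits what the fix can achieve. It does not support the power claims as written.

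The Objective 1 dropout point is small and partly answerable. The 25% combines 13% not returning with 12% lost to weight limits or refused procedures such as scans. Objective 1's grouping rests on BMI, and the Objective 2 contingencies use anthropometry for participants over the scanner limits. If only the 13% are lost, 345 leaves 300 and power is 84.5%; 345 tolerates a loss of 1 − 266/345 = 22.9%. But the Objective 1 text itself states 25%, so Table 5 is wrong on its own terms. The multiplication by 1.25 is inferred: 266 × 1.25 = 332.5, not exactly 334.

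It is also fair that Table 6's method is unknown, and that the section names sources for other inputs from which the SDs might have come. The text does not say that they did, and those sources cannot be seen here.

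**Conclusion.** The concern holds. Tables 5 and 6 use incompatible SDs for the same change score in the same cohort, and nothing in the documents reconciles them. They do not show which SD is right, so the consequences are conditional:

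- **If 69.6 holds:** Objective 2 has about 16% power for its planned difference instead of 80%, and Objective 1 falls slightly short at the stated 25% dropout (78.8% at 345 enrolled).
- **If 24 holds:** Objective 2 is adequately powered at a 1:1 split, and Objective 1's minimum is overstated about eightfold (266 against 34).
- **Under either:** 334 is not the correct minimum for Objective 1. It is far too high at SD 24 and too low at 69.6, where 355 would be needed.

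The 16% rests on a two-sided 0.05 test, equal groups and 258 analysed. The Objective 2 conclusion at SD 69.6 survives any reasonable change to these. The SD conflict is the main point; the dropout error is secondary.

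**What to change.** 1. State the source of each SD and use one value for change in sedentary min/day in both tables. If neither can be sourced, show power for both objectives across SDs from 24 to about 70.
2. If 69.6 is kept, restate Objective 2 as about 16% power for 8.4 min/day (80% for about 24.4) and remove its claim of sufficient power. In Table 5 use N/0.75 (270, 296, 323, 355) and give Objective 1 power as about 77.5% at 334 enrolled and about 79% at 345. Alternatively, justify a lower dropout for Objective 1 and recompute.
3. If 24 is defended, recompute Table 5 with it.
4. State the alpha, sidedness and HFG/LFG percentile split behind Table 6.
5. Leave the cohort size alone, and say that a null Objective 2 result will be interpreted from its confidence interval.

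The cost is revised wording and two recomputed tables. No participants or data are added; what changes is the stated power and how the results may be read.
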